#### **4.2.3 All Causality Grade 3 - 5 AE Incidence Rate**

The third secondary endpoint is the all causality Grade 3 - 5 AE incidence rate defined using NCI CTCAE version 4.0 criteria. The all causality Grade 3 - 5 AE rate is defined as number of subjects who experienced at least 1 AE of Grade 3 or higher with onset on or after the first dose of study treatment and within 30 days of the last dose of study treatment, divided by number of treated subjects.

#### **4.2.4 Pharmacokinetic Analyses**

The fourth secondary endpoint is PK comparisons of nivolumab and ipilimumab administered as FRC to that of sequentially administered nivolumab and ipilimumab. PK will be measured using serum concentration-time data.

#### **4.2.5 Objective Response Rate**

The fifth secondary endpoint is ORR as determined by investigators. The ORR is defined as the number of subjects with a BOR of CR or PR divided by the number of treated subjects. The BOR is defined as the best response designation, as determined by the investigator, recorded between the date of randomization and the date of objectively documented progression per RECIST 1.1 or the date of subsequent anti-cancer therapy including radiotherapy, tumor-directed surgery, or systematic anticancer therapy, whichever occurs first. For subjects without documented progression or first subsequent therapy, all available response designations will contribute to the BOR assessment. For subjects who continue treatment beyond progression, the BOR will be determined based on response designations up to the time of initial RECIST 1.1 progression.

#### **4.2.6 Progression Free Survival**

[figure not shown]
The sixth secondary endpoint is PFS. PFS is defined as the time from the date of randomization to the first date of documented progression, as determined by the investigator per RECIST 1.1, or death due to any cause, whichever occurs first. Clinical deterioration in the absence of progression per RECIST 1.1 is not considered progression for the purpose of determining PFS. Subjects who die without a reported progression will be considered to have progressed on the date of their death. Subjects who did not progress or die will be censored on the date of their last evaluable tumor assessment. Subjects who did not have any on study tumor assessments and did not die will be censored on their date of randomization. Subjects who started any subsequent anti-cancer therapy, including tumor directed radiotherapy, tumor directed surgery, or systematic anticancer therapy, without a prior reported progression will be censored on the date of their last evaluable tumor assessment prior to the initiation of the subsequent anti-cancer therapy.

The progression free survival rate at time T is defined as the probability that a subject has not progressed and is alive at time T following randomization.

Further explanation for various censoring scenarios for the definition of PFS are presented in [Figure 4.2.7-1](#)

Figure 4.2.7-1: Graphic Display of PFS Definition

[Redacted text block]

[REDACTED]

[REDACTED]

[REDACTED]

[REDACTED]

[REDACTED]

[REDACTED]

[REDACTED]

[REDACTED]

[REDACTED]

[REDACTED]

[REDACTED]

[REDACTED]

[REDACTED]

[REDACTED]

[REDACTED]

[REDACTED]

## 5 SAMPLE SIZE AND POWER

Approximately 102 subjects will be randomized to the 2 treatment arms in a 1:1 ratio in order to target 100 treated subjects (50 per arm). This number of treated subjects was chosen to achieve a sufficient level of precision for a descriptive analysis to estimate the difference in rates of AEs in the Broad Scope MedDRA Anaphylactic Reaction SMQ between the two treatment arms. Fifty treated subjects per arm will allow estimation of the rate difference within 95% confidence limits of +/- 20% or less and will be supplemented by a qualitative clinical assessment of the type and severity of events to evaluate benefit-risk. The 20% limit represents what is considered to be a clinically meaningful difference in the rates of infusion-related reactions.

In previously submitted Phase 2/3 studies of nivolumab in combination with ipilimumab (CA209069 and CA209067), AEs in the MedDRA Anaphylactic Reaction SMQ (broad scope) with onset within 2 days after sequential dosing of nivolumab 1 mg/kg combined with ipilimumab 3 mg/kg were reported in 24% of treated subjects. In the current study, if the observed rate of infusion reactions is equal to 24% among 50 treated subjects in each arm, then the 95% CI for the difference in rates between arms will be (-16.7%, 16.7%).

Table 5-1 shows the precision that the sample size of 50 treated subjects per arm will provide for estimating rates and rate differences between the treatment arms under different assumed observed rates.

**Table 5-1: 95% CI for Rates and Rate Differences when Observed in 50 Subjects per Arm**

Observed AE Rate (95% CI)		Observed Rate Difference (95% CI)
Arm A (Co-administration, FRC)	Arm B (Sequential administration)	Arm A - Arm B
24% (13.1%, 38.2%)	22% (11.5%, 36.0%)	2% (-14.5%, 18.5%)
24% (13.1%, 38.2%)	24% (13.1%, 38.2%)	0% (-16.7%, 16.7%)
26% (14.6%, 40.3%)	24% (13.1%, 38.2%)	2% (-15.0%, 19.0%)
30% (17.9%, 44.6%)	28% (16.2%, 42.5%)	2% (-15.8%, 19.8%)
30% (17.9%, 44.6%)	30% (17.9%, 44.6%)	0% (-18.0%, 18.0%)

## **6 STUDY PERIODS, TREATMENT REGIMENS AND POPULATIONS FOR ANALYSES**

### **6.1 Study Periods**

#### **6.1.1 Baseline Period**

##### Study Baseline

Baseline evaluations or events will be defined as evaluations or events that occur before the date and time of the first dose of study treatment. Evaluations on the same date and time of the first dose of study treatment will be considered as baseline evaluations.

In cases where the time (onset time of event or evaluation time and dosing time) is missing or not collected, the following definitions will apply:

- Pre-treatment AEs will be defined as AEs with an onset date prior to but not including the day of the first dose of study treatment
- Baseline evaluations (laboratory tests, pulse oximetry and vital signs) will be defined as evaluations with a date on or prior to the day of first dose of study treatment

If there are multiple valid assessments, the assessment that is closest to day (and time if collected) of the first dose of study treatment will be used as the baseline in the analyses. If multiple assessments are collected at the same date (and time if collected), the assessment with the latest database entry date (and time if collected) will be considered as baseline.

If more than one tumor biopsy specimen is available, baseline PD-L1 expression will be determined from the most recently collected specimen (prior to first dose of study treatment) with a measurable result. If all specimens for a given subject are either indeterminate or unknown, then the PD-L1 expression will be considered indeterminate as long as at least one specimen is indeterminate. Otherwise, PD-L1 expression will be considered unknown.

#### **6.1.2 Post Baseline Period**

On-treatment AEs will be defined as AEs with an onset date-time on or after the date-time of the first dose of study treatment (or with an onset date on or after the day of first dose of study treatment if time is not collected or is missing). An AE will be counted as on-treatment if the event occurred within 30 days (or 100 days depending on analysis) of the last dose of study treatment.

On-treatment evaluations (laboratory tests, pulse oximetry and vital signs) will be defined as evaluations taken after the day (and time, if collected and not missing) of first dose of study treatment. An evaluation will be counted as on-treatment if it occurred within 30 days (or 100 days depending on analysis) of the last dose of study treatment.

The Post Baseline Period may be further divided into the following sub-periods.

### **6.1.2.1 Part 1 Treatment Period (Combination Portion)**

Part 1 dosing is defined as any medication recorded on ‘Record of Study Medication’ CRF page with a visit label containing the text ‘Cycle 1’, ‘Cycle 2’, ‘Cycle 3’, or ‘Cycle 4’ and with total dose delivered > 0 mg.

On-treatment AEs during the Part 1 Treatment Period will be defined as AEs with an onset date-time on or after the date-time of the first dose of Part 1 study treatment (or with an onset date on or after the day of first dose of Part 1 study treatment if time is not collected or is missing). An AE will be counted as on-treatment during Part 1 if the event occurred within 30 days of the last dose of Part 1 study treatment.

On-treatment evaluations (laboratory tests) during Part 1 will be defined as evaluations taken after the day (and time, if collected and not missing) of first dose of Part 1 study treatment. An evaluation will be counted as on-treatment during Part 1 if it occurred within 30 days of the last dose of Part 1 study treatment.

### **6.1.2.2 Part 2 Treatment Period (Maintenance Portion)**

Part 2 dosing is defined as any medication recorded on ‘Record of Study Medication’ CRF page with a visit label containing the text ‘Part 2’ and with total dose delivered > 0 mg.

On-treatment AEs during the Part 2 Treatment Period will be defined as AEs with an onset date-time on or after the date-time of the first dose of Part 2 study treatment (or with an onset date on or after the day of first dose of Part 2 study treatment if time is not collected or is missing). An AE will be counted as on-treatment if the event occurred within 30 days (or 100 days depending on analysis) of the last dose of Part 2 study treatment.

On-treatment evaluations (laboratory tests) during Part 2 will be defined as evaluations taken after the day (and time, if collected and not missing) of first dose of Part 2 study treatment. An evaluation will be counted as on-treatment if it occurred within 30 days (or 100 days depending on analysis) of the last dose of Part 2 study treatment.

## **6.2 Treatment Regimens**

The treatment group **”as randomized”** will be retrieved from the IVRS system:

- Arm A (Co-Administration, FRC): Experimental arm: BMS-986237 administered every 3 weeks for 4 doses followed by nivolumab flat dose 480 mg every 4 weeks
- Arm B (Sequential): Control arm: nivolumab 3 mg/kg + ipilimumab 1 mg/kg administered every 3 weeks for 4 doses followed by nivolumab flat dose 480 mg every 4 weeks

The treatment group **“as treated”** will be the same as the **“as randomized”** unless the subject received the incorrect drug for **the entire period** of treatment, in which case the subject’s treatment group will be defined as the incorrect drug the subject actually received.

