## 4 ENDPOINTS

### 4.1 Primary Endpoint: MedDRA Anaphylactic Reaction Broad Scope SMQ AE Incidence Rate

The primary endpoint of the study is the incidence of AEs in the Broad Scope MedDRA Anaphylactic Reaction SMQ occurring within 2 days after dosing during the combination, Part 1 period. This incidence rate is defined as number of subjects who experienced at least 1 AE in the MedDRA Anaphylactic Reaction broad scope SMQ with onset on the day of or within 2 days after any study therapy infusion during the combination period (Part 1) divided by number of treated subjects. For reference, the terms currently included in the MedDRA Anaphylactic Reaction SMQ based on MedDRA version 19.0 are listed in [Table 4.1-1](#).

The analysis of the primary endpoint will occur when all subjects who are still on-treatment complete Part 1 period.

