## **7 STATISTICAL ANALYSES**

### **7.1 General Methods**

Unless otherwise noted, the following subsections describe tabulations of discrete variables, by the frequency and proportion of subjects falling into each category, grouped by treatment (with total). Percentages given in these tables will be rounded and, therefore, may not always sum to 100%. Continuous variables will be summarized by treatment group (with total) using the mean, standard deviation, median, minimum and maximum values. If a missing category is not being presented in the data display, only those subjects with non-missing values for the parameter being assessed are included in the percentage calculation.

Time to event distribution will be estimated using Kaplan Meier techniques. This will be done for endpoints progression free survival, overall survival and duration of response (note that TTR will be analyzed using summary statistics such as mean, SD, median, min, max). Median survival time along with 95% CI will be constructed based on a log-log transformed CI for the survivor function  $S(t)$ . Rates at fixed time points will be derived from the Kaplan Meier estimate and corresponding confidence interval will be derived based on Greenwood formula for variance derivation and on log-log transformation applied on the survivor function  $S(t)$ .

Confidence intervals for binomial proportions will be derived using the Clopper-Pearson method.

Formal hypothesis testing with control of Type I error will not be conducted for any of the endpoints in this study. No p-values will be presented. Confidence intervals, when presented, will be for descriptive purposes only and will not be adjusted for multiplicity.

Unless otherwise noted, safety analyses will be performed using the on-treatment definition for the entire study treatment period (i.e. combined Part 1 and Part 2 treatment periods) as defined in [Section 6.1.2](#). Alternate analysis periods will be used for specific endpoints or selected analyses as described in the corresponding endpoint or analysis section of this SAP.

Please see the following sections for additional details:

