#### **7.2.2 Relevant Protocol Deviations**

The following programmable deviations will be considered as relevant protocol deviations and summarized by treatment group and overall. Non-programmable relevant eligibility and on

treatment protocol deviations, as well as significant (both programmable and non programmable) eligibility and on-treatment protocol deviations will be reported through ClinSIGHT listings.

At Entrance:

- Subjects with baseline KPS < 70%
- Subjects who received prior systemic anti-cancer treatment in the metastatic setting
- Subjects without histologically confirmed RCC with a clear-cell component, documented advanced or metastatic (AJCC Stage IV) RCC

On-study:

- Subjects receiving anti-cancer therapy (chemotherapy, hormonal therapy, immunotherapy, standard or investigational agents for treatment of cancer) while on study therapy
- Subjects treated differently than as randomized (subjects who received the wrong treatment, excluding the never treated)

Listings will also be provided.

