**Table 7.4.1-2: Study Therapy Parameter Definitions During Part 2 (Maintenance)**

	Nivolumab (Arms A and B)
Dosing Schedule per Protocol	480 mg flat dose every 4 weeks
Dose	Dose (mg) = total dose delivered as recorded on Record of Study Medication CRF
Cumulative Dose	Cum Dose (mg) is the sum of the doses administered to a subject during Part 2.
Relative Dose Intensity (%)	$[\text{Cum dose (mg)} / ((\text{Last dose date in Part 2} - \text{First dose date in Part 2} + 28) \times 480/28)] \times 100$
Infusion Duration (mins)	Each infusion duration is calculated as infusion stop date/time - infusion start date/time.
Duration of Treatment	last dose date in Part 2- first dose date in Part 2 + 1

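### The as-treated rule in SAP 6.2, read literally, lets Part 2 nivolumab (identical in both arms) decide which arm a participant's Part 1 events are counted in

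*SAP*

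**What the plan says.** SAP 6.2 takes the randomized group from the IVRS and sets the as-treated group equal to it "unless the subject received the incorrect drug for the entire period of treatment". The emphasis on the entire period is the SAP's own, but the section does not say which period is meant.

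The same section describes each arm as four Part 1 administrations "followed by nivolumab flat dose 480 mg every 4 weeks". SAP Table 7.4.1-2 gives one Part 2 schedule, "480 mg flat dose every 4 weeks", in a single column for both arms.

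SAP 7.1, in setting the default window for safety analyses, refers to the "entire study treatment period (i.e. combined Part 1 and Part 2 treatment periods").

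The primary endpoint in SAP 4.1 counts participants with a qualifying event "with onset on the day of or within 2 days after any study therapy infusion during the combination period (Part 1"). SAP 7.6.1 reports it by treatment arm in all treated subjects and does not say whether arm means as treated or as randomized. SAP 7.3.1 (disposition) and 7.4 (exposure) do name the as-treated grouping.

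SAP 7.2.2 lists as a relevant deviation "Subjects treated differently than as randomized (subjects who received the wrong treatment, excluding the never treated"). It attaches no consequence for the grouping of the primary endpoint.

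**The concern.** The arms differ only in Part 1, and the primary endpoint looks only at Part 1. A rule that needs the drug to be incorrect throughout treatment, when Part 2 can never be incorrect, lets the part of the trial that carries no information about the comparison settle the classification.

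Two consequences follow on the literal reading. First, an Arm B participant who received only FRC in Part 1 and went on to Part 2 would have any reaction to FRC counted under sequential dosing, and the reverse for Arm A. Secondly, two participants with the same wrong Part 1 dosing would be grouped differently according to whether they reached Part 2. Reaching Part 2 is a post-baseline outcome that toxicity can affect.

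The PK comparison in SAP 7.7 is also summarized by treatment arm, so FRC concentrations could appear under sequential administration. The trial exists to compare one infusion with two, so the grouping should follow what was infused in Part 1.

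**Working it through.** **Step 1: apply the rule.** Take a participant randomized to Arm B who receives FRC at every Part 1 cycle.

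| Course after Part 1 | Incorrect drug throughout? | As-treated arm, literal reading |
|---|---|---|
| Stops before Part 2 | Yes | A (product received) |
| Takes one or more Part 2 doses | No, since Part 2 nivolumab is correct for either arm | B (as randomized) |

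If SAP 7.6.1 instead means as randomized, both participants are analysed in Arm B.

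**Step 2: reproduce the plan's figure.** SAP Section 5 gives 50 treated per arm, 24% observed in each arm (12/50), and a 95% CI for the difference of (-16.7%, 16.7%). The unpooled Wald interval is

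d ± 1.96 × √(pA·qA/nA + pB·qB/nB), with q = 1 - p.

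Here d = 0 and the half-width is 1.96 × √(2 × 0.24 × 0.76/50) = 1.96 × 0.0854 = 0.167. This reproduces. All five rows of SAP Table 5-1 reproduce in the same way.

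**Step 3: size of one case.** Assumption: the SAP grouping gives 12/50 v 12/50, and k Arm B participants in fact received only FRC in Part 1 and entered Part 2. The documents give no value for k. Regrouping by Part 1 product received:

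| k | Events among the k | Arm A | Arm B | Difference, points (95% CI) |
|---|---|---|---|---|
| 1 | 1 | 13/51 = 25.5% | 11/49 = 22.4% | +3.0 (-13.7, 19.8) |
| 1 | 0 | 12/51 = 23.5% | 12/49 = 24.5% | -1.0 (-17.7, 15.8) |
| 2 | 2 | 14/52 = 26.9% | 10/48 = 20.8% | +6.1 (-10.6, 22.7) |
| 2 | 0 | 12/52 = 23.1% | 12/48 = 25.0% | -1.9 (-18.7, 14.9) |

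These intervals are unstratified. The planned analysis uses CMH weighting by IMDC score, so they are illustrations only.

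**Step 4: expected shift.** The +3.0 is conditional on an event. Averaging the two k = 1 rows at the SAP's 24% rate: 0.24 × 3.04 + 0.76 × (-0.96) = 0.73 - 0.73 = 0.

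**Step 5: systematic attenuation.** If one of 50 in Arm B truly received FRC, the expected Arm B rate is pB + (pA - pB)/50. The expected difference shrinks by (pA - pB)/50. At a true difference of 20 points, the SAP's clinically meaningful limit, that is 20/50 = 0.4 points.

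**Step 6: timing.** With Part 1 doses at weeks 0, 3, 6 and 9 and a 6-week gap, Part 2 starts at about week 15. The SAP's Schedule of Analyses puts the primary analysis about 3 months after accrual ends: 3 × 30.4375/7 = 13.0 weeks. A late-enrolled wrong-product participant could thus be in the received arm at the primary analysis and in the randomized arm at the final one.

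**The case against.** The strongest reply is that the SAP never says the 6.2 rule governs the primary comparison. SAP 7.6.1 names no grouping, and much of the safety analysis defers to a Core Safety SAP that is not among the documents and could override it. A reader might infer that wrong-product participants who enter Part 2 are definitely counted in the wrong arm under the as-treated rule. The documents do not establish that. What stands is that neither possible grouping protects the comparison for these participants, and the text does not choose between them.

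It can also be said that incorrect drug has meaning only where the arms differ, so the period should be read as Part 1, which SAP 6.1.2.1 defines separately. The 7.1 wording concerns the adverse-event window and not arm assignment. That reading is reasonable and would remove the problem, but 6.2 does not state it and the nearest parallel wording points the other way.

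A reader might infer a bias of 3 points toward no difference. Steps 4 and 5 do not support it: the sign depends on whether the participant had an event, the expected shift at equal 24% rates is about zero, and attenuation appears only if the arms truly differ.

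A reader might also infer that the primary result could change between data cuts. The primary endpoint is scheduled once, so the switch in step 6 would affect only the safety summaries repeated at the final analysis.

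Finally, the scenario is remote. The trial is open-label, the arms differ visibly in the number of infusions, the FRC vial label is distinctive (Protocol Table 7-2), and IRT assigns vials at each Part 1 visit (Protocol Table 2-2). Any case would appear in the deviation summary and the by-subject dosing listing. All of this stands and bears on severity. It does not make the rule clear.

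**Conclusion.** The point holds as a low-severity defect of definition. Read literally, SAP 6.2 keeps a participant with wholly wrong Part 1 dosing in the randomized arm once any Part 2 dose is given, and reassigns an otherwise identical participant who stopped earlier. Together with the unnamed grouping in 7.6.1, this means that Part 1 events could be counted under the product not received.

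The effect is about +3.0 or -1.0 points per participant on the observed difference, with or without an event, and about 0.4 points of expected attenuation at a true 20-point difference. The planned half-width is 16.7 points. The analysis is descriptive, with no formal testing, so no error rate is affected.

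The conclusion assumes that the period in 6.2 means all of treatment and that the Core Safety SAP contains no overriding rule. The number of cases is unknown and may be zero.

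**What to change.** In SAP 6.2, define as treated from Part 1 doses only: the randomized arm, unless all Part 1 doses the participant received were the other arm's product. Say that Part 2 nivolumab cannot change this assignment.

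In SAP 7.6.1, 7.6.2 and 7.7, state that the arms are as treated on this definition.

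Participants with only some wrong Part 1 doses stay as randomized under both the present rule and this one. That choice should be stated openly, with such cases identified through the existing deviation listing.

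The cost is a sentence in each section and a line of derivation code. No new data are needed.

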### 6.3 Populations for Analyses

Since the primary objective will be addressed by a safety endpoint, the primary endpoint analysis will be based on all treated subjects. For consistency, the secondary endpoints will use the same analysis population as the primary endpoint (ie, all treated subjects).

Population	Description
All Enrolled Subjects	All subjects who signed an informed consent form and were registered into the IRT.
All Randomized Subjects	All subjects who were randomized to any treatment group. This is the primary dataset for efficacy listings.
All Treated Subjects	All subjects who received at least one dose of any study medication. This is the primary dataset for analysis of study conduct, study population, efficacy (including secondary endpoints), exposure, and safety (including primary endpoint).
All Treated Subjects in Part 2	All subjects who received at least one dose of study medication in the open-label nivolumab flat dose maintenance phase (Part 2).
Response-Evaluable Subjects	All treated subjects with measurable disease at a baseline tumor assessment and at least one on-treatment tumor assessment.
Pharmacokinetic Subjects	All treated subjects with available serum time-concentration data.
Immunogenicity Subjects	
All treated subjects with available ADA data.
 
 
- Nivolumab ADA evaluable subjects: all treated subjects with baseline and at least 1 postbaseline nivolumab immunogenicity assessment.
 
- Ipilimumab ADA evaluable subjects: all treated subjects with baseline and at least 1 postbaseline ipilimumab immunogenicity assessment.
 

[REDACTED]	
[REDACTED]
 
 
■ [REDACTED]
 
■ [REDACTED]
 
■ [REDACTED]
 

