### 2.3 Blinding and Unblinding

This is an open-label study.

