### **7.5.2 Progression Free Survival**

PFS curves for each treatment group will be estimated using the Kaplan-Meier (KM) product limit method in All Treated Subjects. Median PFS and corresponding two-sided, 95% confidence intervals will be computed. Descriptive HRs and corresponding two sided 95% CIs for Arm A relative to Arm B will be estimated using a Cox proportional hazards model, with treatment group as a single covariate, stratified by IMDC prognostic score at screening (IVRS source). PFS rates at 6 months with 95% CIs will be estimated using KM methodology.

The source of progression event (death versus progression) will be summarized by treatment group.

The status of subjects who are censored in the PFS KM analysis will be tabulated for each treatment group using the following categories:

- On-study (on-treatment, in follow-up)
- Off-study (lost to follow-up, withdrawn consent, never treated)
- Received subsequent anticancer therapy

[REDACTED]

Survival rates at 6 months will be estimated using KM estimates on the OS curve for each treatment group. Associated two-sided 95% CIs will be calculated.

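### ORR and PFS run from randomization and are compared between arms, but only in treated subjects, so anyone lost before the first dose leaves the efficacy comparison; the planned effect is small and the repair is cheap

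*SAP*

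**What the plan says.** SAP 6.3 and protocol 10.2 choose the treated population because the primary endpoint is a safety endpoint, and extend it to efficacy: "For consistency, the secondary endpoints will use the same analysis population as the primary endpoint (ie, all treated subjects". Treated is defined as "All subjects who received at least one dose of any study medication". Of the All Randomized set, SAP 6.3 says: "This is the primary dataset for efficacy listings".

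SAP 4.2.5 follows this: "The ORR is defined as the number of subjects with a BOR of CR or PR divided by the number of treated subjects". SAP 7.5.2 estimates the PFS curves in All Treated Subjects. Protocol 10.3.1 also uses treated participants as the ORR denominator.

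The clocks start earlier. Best overall response is the best designation "recorded between the date of randomization and the date of objectively documented progression per RECIST 1.1" (or subsequent therapy, if sooner). For PFS, SAP 4.2.6 says: "PFS is defined as the time from the date of randomization to the first date of documented progression".

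SAP 7.5.1 and 7.5.2 specify between-arm contrasts: a CMH odds ratio and ORR difference, and a stratified Cox hazard ratio, all using the IVRS stratum. SAP 2.3 says: "This is an open-label study". The table of censored PFS subjects in SAP 7.5.2 includes the row "Off-study (lost to follow-up, withdrawn consent, never treated".

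**The concern.** A safety endpoint is properly analysed in those who were exposed. That reasoning does not carry over to a comparison of efficacy between randomized arms, and consistency is the only reason the plan gives.

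Receiving a first dose happens after randomization, and in an open-label trial the arm can be known by then. Requiring a dose is a post-randomization exclusion that could depend on the arm. For ORR it works in one direction: an undosed subject leaves the denominator instead of counting as a non-responder, so the arm with more pre-dose losses looks better.

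Two drafting gaps add to this. The never-treated row cannot be filled in a population of treated subjects. SAP 6.2 defines both as-randomized and as-treated groups, and the disposition and exposure sections say which applies, but the visible efficacy text in SAP 7.5 does not.

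**Working it through.** **Inputs**
- 102 randomized 1:1 to give 100 treated, with 1.5% attrition (protocol synopsis, Number of Participants; SAP 5). This is 51 per arm.
- First dose due within 72 hours of randomization (protocol Tables 2-1 and 2-2).
- Subjects alive with no on-study tumor assessment are censored at randomization (SAP 4.2.6).
- The documents give no expected ORR. I assume 30 to 50%, equal among treated subjects in both arms, with undosed subjects as non-responders.

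**The plan's own figures reproduce**
- Randomized: 100 / (1 − 0.015) = 101.5, rounded up to 102. Expected undosed: 102 × 0.015 ≈ 1.5, or 2 as planned.
- SAP Table 5-1, 24% in each arm of 50: 1.96 × √(2 × 0.24 × 0.76 / 50) = 16.7 points, as stated. The same formula is used below.

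**Shift in the ORR difference**

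With k undosed in an arm of 51 and ORR p among the treated, the as-randomized ORR is p × (51 − k) / 51, a fall of p × k / 51.

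- One loss per arm: both ORRs are multiplied by 50/51, so with equal ORRs the difference moves by 0.
- Both losses in one arm:

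| Assumed ORR | As-randomized ORR, k = 2 | Shift in difference | 95% CI half-width, 50 per arm |
|---|---|---|---|
| 30% | 28.8% | 1.2 points | 18.0 points |
| 40% | 38.4% | 1.6 points | 19.2 points |
| 50% | 48.0% | 2.0 points | 19.6 points |

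At an ORR of 20% the shift is 0.2 × 2/51 = 0.8 points and the half-width 15.7 points, so over 20 to 50% the half-width runs from about 16 to 20 points. The worst planned case is about a tenth of it (2.0 / 19.6).

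- Loss beyond the plan, for scale only: five undosed in one arm gives 0.3 × 5/51 = 2.9 points to 0.5 × 5/51 = 4.9 points.

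**PFS**

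An undosed subject who is alive without a scan is censored at time zero, is in no later risk set and adds nothing to the hazard ratio. The hazard ratio changes only through undosed subjects who are scanned or whose death is recorded.

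**The case against.** The choice is disclosed, pre-specified and the same in protocol and SAP. The trial asks a safety question. ORR and PFS are the fifth and sixth secondary endpoints, and SAP 7.1 rules out formal testing and p-values and treats intervals as descriptive. Both arms are assigned the same two antibodies at the same mg/kg doses and schedule, so a motive for arm-dependent withdrawal within 72 hours is not obvious. SAP 7.3.1 tabulates randomized-but-untreated subjects with reasons by arm, so a reader could rebuild the as-randomized ORR denominator. Listing all randomized subjects while summarizing treated ones is not in itself a contradiction.

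All of this stands, and it lowers the importance of the point. It does not supply the missing analysis: a tabulation leaves the reader to derive a contrast that the SAP could report.

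A reader might infer that anyone who drops out once the arm is known is lost from the comparison. The documents do not support that. One dose keeps a subject in: as a non-responder for ORR if no response is recorded, and under the censoring rules for PFS. Only losses between randomization and first dose are removed.

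It is also fair to say that an all-randomized PFS analysis may gain little. In protocol Table 2-4 the first follow-up visits are tied to the last dose, and the visible schedule sets out no specific tumor follow-up for subjects who were never dosed.

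**Conclusion.** The point holds as a limited one. The efficacy contrasts start at randomization but exclude subjects by a later event, for a reason that belongs to the safety analysis. At the planned loss of about 2 of 102 the ORR difference moves by 0 to about 2.0 points, well inside its sampling error, and the PFS hazard ratio is almost unchanged.

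These sizes rest on an assumed ORR of 30 to 50%, equal in both arms, and on the planned attrition. The effect would matter more only if pre-dose loss proved larger and uneven, which the documents neither predict nor rule out. They give no evidence that loss will differ by arm, so it would be too strong to conclude that the planned efficacy results are materially biased. The case for acting is that the safeguard costs little and should be fixed before the losses are known.

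**What to change.** - **ORR (SAP 4.2.5, 6.3, 7.5.1).** Compute the difference and odds ratio in All Randomized Subjects, grouped as randomized, with undosed subjects as non-responders. Make this the main analysis, or at least a pre-specified analysis beside All Treated. Align protocol 10.2 and 10.3.1 if the main set changes.
- **PFS (SAP 7.5.2).** Apply the existing censoring rules to all randomized subjects, using whatever follow-up exists.
- **Grouping (SAP 7.5).** State that efficacy is grouped as randomized.
- **Never-treated row (SAP 7.5.2).** Keep it if the table covers all randomized subjects; remove it if the table stays with treated subjects.
- **Safety.** Leave the safety analyses in All Treated Subjects.

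The cost is wording and one further set of outputs. ORR needs no new data. The downside is a slightly lower reported ORR: with one undosed subject in an arm of 51, 40.0% becomes 40.0 × 50/51 = 39.2%.
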